**Virologic failure = On-treatment virologic failure or Relapseoverall.**

Only subjects who have at least one post-treatment HCV RNA value will be included in analyses of relapse. For the analysis of relapse, completion of treatment is defined as a study drug duration of 77 days or greater for subjects assigned to 12 weeks of treatment, and 154 days or greater for subjects assigned to 24 weeks of treatment. If the last available post-treatment value is  $\geq$  LLOQ, then the subject will be considered a relapse (i.e., will not require confirmation).

HCV reinfection is defined as confirmed HCV RNA  $\geq$  LLOQ after the end of treatment in a subject who had HCV RNA  $<$  LLOQ at Final Treatment Visit, along with the post-treatment detection of a different HCV genotype, subtype, or clade compared with baseline, as determined by phylogenetic analysis of the NS3 or NS5A, and/or NS5B gene sequences. Reinfection in the case of the same HCV subtype is defined as a clade switch, as indicated by the lack of clustering between the baseline and post-treatment sequences by phylogenetic analysis. If phylogenetic analysis is not possible due to technical difficulties, HCV reinfection may be determined with a confirmed HCV genotype or subgenotype switch by the Versant HCV Genotype Inno-LiPA Assay v2.0 or Sanger assay.

Post-treatment relapse is defined as described earlier (**Relapse12**, **Relapse24**, **Relapseoverall**), and no genotype, subtype, or clade switch compared with baseline as determined by phylogenetic analysis of the NS3 or NS5A gene sequences. If phylogenetic analysis is not possible due to technical difficulties, the subject will be defined as having a post-treatment relapse unless an HCV genotype or subtype switch is confirmed by the Versant HCV Genotype Inno-LiPA Assay v2.0 or Sanger assay.

### **Reasons for SVR12 Non-Response**

Subjects who do not achieve SVR12 (SVR12 non-responders) will be categorized as having:

1. On-treatment virologic failure (see **On-treatment virologic failure definition**);
2. HCV reinfection (see definition described earlier);
3. Relapse12;
4. Prematurely discontinued study drug with no on-treatment virologic failure (defined as any SVR12 non-responder who prematurely discontinued study drug [study drug duration < 77 days for subjects assigned to 12 weeks of treatment or duration < 154 days for subjects assigned to 24 weeks of treatment] and did not meet the **On-treatment virologic failure or HCV reinfection definitions**);
5. Missing follow-up data in the SVR12 window (defined as any subject who completed study drug without data in the SVR12 window after applying the imputation rules and not meeting the definitions of [1], [2], [3], or [4]);
6. Other (defined as SVR12 non-responder not meeting the definitions of [1] – [5]).

### **Reasons for SVR24 Non-Response**

Subjects who do not achieve SVR24 (SVR24 non-responders) will be categorized as having:

1. On-treatment virologic failure (see **On-treatment virologic failure definition**);
2. HCV re-infection;
3. Relapse12;
4. Relapse24;
5. Prematurely discontinued study drug with no on-treatment virologic failure (defined as any SVR24 non-responder who prematurely discontinued study drug

---

[study drug duration < 77 days for subjects assigned to 12 weeks of treatment or duration < 154 days for subjects assigned to 24 weeks of treatment] and did not meet the **On-treatment virologic failure, HCV reinfection, Relapse12, or Relapse24** definitions);

6. Missing follow-up data in the SVR24 window (defined as any subject who completed study drug without data in the SVR24 window after applying the imputation rules, and not meeting the definitions of [1], [2], [3], [4], or [5]);
7. Other (defined as SVR24 non-responder not meeting the definitions of [1] – [6]).

For the reasons for SVR12 and SVR24 nonresponse defined above, subjects are only to be counted in 1 category. Specifically, subjects who were SVR12 or SVR24 nonresponders meeting the definition of HCV reinfection will be counted in the reinfection category regardless of whether they meet the definition of prematurely discontinued study drug, relapse12 or relapse24.

## **10.2 Handling of Multiplicity**

This study will proceed using a sequential testing procedure from testing the hypothesis for the primary efficacy endpoint that the SVR12 rate is 20% > than the pre-specified historical control rate of 47% to the hypothesis for the secondary efficacy endpoint that the SVR24 rate is 20% > than the pre-specified historical control rate of 47%. Thus, the testing of the secondary hypothesis regarding SVR24 will only be performed in the lower confidence bound of the 2-sided 95% confidence interval of the SVR12 rate is > 67%.

## **10.3 Primary PK and Primary Efficacy Analysis**

### **10.3.1 Primary PK Analysis**

The primary PK endpoints from Part 1 are:

- Cmax and AUC following dosing on Week 2, and trough concentration following dosing on Week 2 and Week 8 for OBV, PTV, DSV, and RTV.

---

For the intensive PK data at Week 2, the pharmacokinetic parameters of  $C_{max}$ ,  $T_{max}$  and AUC will be calculated and summarized for each analyte (paritaprevir, ombitasvir, ritonavir, dasabuvir, and dasabuvir M1 metabolite, and RBV, as applicable based on DAA regimen).

The trough concentrations at Week 8 will be summarized for each analyte.

### **10.3.2 Primary Efficacy Analysis Across Parts 1 and 2.**

The primary efficacy endpoint across Parts 1 and 2 is:

- The percentage of subjects with  $SVR_{12}$  among all subjects.

The  $SVR_{12}$  rate and corresponding 2-sided 95% confidence interval will be presented.

For both the primary and secondary efficacy endpoints, the Wilson's score method will be used to calculate the confidence interval.

According to the Highlights of Prescribing Information of PEGASYS®, the  $SVR_{24}$  rate was 47% among 45 treatment-naïve pediatric subjects with HCV GT1 in the NV17424 trial. To show that the DAA regimen is superior to this current standard of care by 20%, the lower bound of the 2-sided 95% confidence interval of the  $SVR_{12}$  rate across all subjects in the study must be greater than 67%.

### **10.4 Secondary Efficacy Analyses Across Parts 1 and 2**

The secondary efficacy endpoints calculated across subjects in Parts 1 and 2 are:

1. The percentage of subjects who achieve  $SVR_{12}$  by formulation, age and weight group, and across all subjects on the adult formulation.
2. The percentage of subjects who achieve  $SVR_{24}$  by formulation, age and weight group, and across all subjects on the adult formulation.
3. The percentage of subjects with ALT normalization during treatment, defined as  $ALT \leq ULN$  at the final treatment visit for subjects with  $ALT > ULN$  at baseline,

---

by formulation, age and weight group, and across all subjects on the adult formulation.

For the percentage of subjects with SVR12 or SVR24 and the percentage of subjects with ALT normalization during treatment, the simple percentage will be calculated along with the 2-sided 95% confidence intervals.

To test the hypothesis that the percentage of HCV pediatric subjects treated with ombitasvir/paritaprevir/r, with or without dasabuvir with or without RBV who achieve SVR24 is superior to the historical SVR rate of 47% for the pediatric population treated with pegIFN and RBV by 20%, the lower bound of the 2-sided 95% confidence interval of the SVR24 rate across all subjects in the study will also be compared to 67%.

ALT normalization is defined as the percentage of subjects with ALT at or below the ULN at the final treatment visit among subjects with ALT > ULN at baseline, and will be presented along with 95% confidence intervals.

The concordance between SVR12 and SVR24 will be assessed by agreement between SVR12 and SVR24 and by the positive predictive value (PPV) and the negative predictive value (NPV) of SVR12 on SVR24. The agreement between SVR12 and SVR24 is defined as the number of subjects achieving both SVR12 and SVR24 and the number of subjects not achieving both SVR12 and SVR24 out of all subjects in the ITT population. The PPV of SVR12 on SVR24 is the proportion of subjects who achieve SVR24 out of all subjects who achieved SVR12. The NPV of SVR12 on SVR24 is the proportion of subjects who do not achieve SVR24 out of all subjects who do not achieve SVR12.

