### **Missing Data Imputation for SVR**

HCV RNA values will be selected for analysis based on the analysis windows defined in Section 6.3.

For analyses of SVR, subjects' missing visit values will have backward imputation applied, if possible. For backward imputation, if the nearest HCV RNA value after the SVR window is unquantifiable or undetectable, then it will be used to impute the HCV RNA value in the SVR window. If a subject is missing an HCV RNA value within the appropriate SVR window after performing backward imputation, then this value will be imputed with an HCV RNA value from a local laboratory if present; otherwise, the HCV RNA value will be missing. Subjects with missing HCV RNA data in the analysis window, after imputations, will be imputed as a failure.

Regardless of the imputation method described above, if a subject starts another treatment for HCV, then all HCV RNA values for this subject measured on or after the start date of the new HCV treatment will be excluded from analyses. The subject will be considered a failure for summaries of viral response at all time points after the start of the new HCV treatment.

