## **10.0                   Efficacy Analysis**

### **10.1                   General Considerations**

All efficacy analyses will be performed in the ITT population, unless otherwise specified.

Missing data will be imputed as described in Section 6.3 for analyses of the HCV RNA endpoints of SVR.

Plasma HCV RNA levels will be determined for each sample collected by the central laboratory using the Roche COBAS® AmpliPrep/COBAS® TaqMan® HCV Quantitative Test, v2.0. The lower limit of detection (LLOD) and lower limit of quantification (LLOQ) for this assay (regardless of genotype) are both 15 IU/mL.

HCV RNA results that are detectable but not quantifiable are reported as "< 15 IU/ML HCV RNA DETECTED" and those that are undetectable are reported as "HCV RNA NOT DETECTED" in the database.

The notation "HCV RNA < LLOQ" is used to represent all HCV RNA values < 15 IU/mL, including values reported as "HCV RNA NOT DETECTED" or "< 15 IU/ML HCV RNA DETECTED." HCV RNA  $\geq$  LLOQ are all quantifiable values of 15 IU/mL or greater.

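### SVR12/SVR24 concordance is planned only on imputed response status, so it mixes true late relapse with missed visits; an observed-pair version should be added.

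*SAP*

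**What the plan says.** SAP 10.4 defines three concordance measures. Agreement is the number of subjects with the same status at both time points, "out of all subjects in the ITT population". PPV is the share reaching SVR24 "out of all subjects who achieved SVR 12". NPV is the share not reaching SVR24 "out of all subjects who do not achieve SVR 12". None of the three requires a measured HCV RNA value in both windows.

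SAP 10.1 sets the data rules: "All efficacy analyses will be performed in the ITT population, unless otherwise specified", and "Missing data will be imputed as described in Section 6.3 for analyses of the HCV RNA endpoints of SVR". SAP 6.3 then works in order. First, "if the nearest HCV RNA value after the SVR window is unquantifiable or undetectable, then it will be used to impute" the value in the SVR window. Next, a local-laboratory value may be used. Last, "Subjects with missing HCV RNA data in the analysis window, after imputations, will be imputed as a failure". Separately, values on or after the start of a new HCV treatment are dropped, and the subject counts as a failure from then on.

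SAP 10.1 also denies SVR24 to anyone with a confirmed quantifiable post-treatment value before or during the SVR24 window. It defines Relapse24 only for SVR12 achievers who have HCV RNA data in that window, excluding reinfection; SAP 10.7 lists its analysis. Missing SVR24 data is its own non-response category (10.1), tabulated under 10.8.

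**The concern.** Counting missing data as failure is a cautious rule for estimating a response rate. It suits less well the question of whether one measurement predicts a later one, because it assigns an outcome to subjects who were not measured. Three things follow from the text:

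- An SVR12 achiever with no later sample becomes an SVR24 failure and enters the table as discordant, exactly like a late relapse.
- A subject lost before Week 12 fails both endpoints and enters as agreement and as a correct negative, with neither outcome observed.
- A subject with no value in the SVR12 window but a Week 24 value below LLOQ has SVR12 filled from Week 24. One measurement then supplies both halves of the pair, and they must agree.

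At stake is how the concordance table is read. With about 62 subjects planned, a few missed visits could look like failure of SVR12 to predict SVR24.

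**Working it through.** **Figure in the plan.** The SAP gives no figure for concordance, PPV or NPV, so there is none to reproduce. The only related design figure is power above 90% with 50 or more subjects at a true SVR12 rate of 90%. It reproduces: with N = 50, exact binomial power is 99.1% for the normal-approximation bound (at least 40 responders) and 97.5% for the Wilson bound (at least 41). It does not bear on this point beyond supplying the 90%.

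**Inputs.** N = 62 (SAP 4.2). SVR12 achievers S = 0.90 × 62 = 55.8, taken as 56 (rate from SAP 4.3). Non-achievers F = 62 − 56 = 6. Assumed: k = achievers with no HCV RNA from the SVR24 window onward; x = late relapses among the rest.

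**Formulas under the SAP rules.** PPV = (S − k − x)/S. Agreement = (S − k − x + F)/N. NPV = F/F. PPV among achievers with SVR24 data = (S − k − x)/(S − k).

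| k | x | PPV, SAP rules | PPV, SVR24 data present | Agreement, SAP rules |
|---|---|---|---|---|
| 1 | 0 | 55/56 = 98.2% | 55/55 = 100% | 61/62 = 98.4% |
| 0 | 1 | 55/56 = 98.2% | 55/56 = 98.2% | 61/62 = 98.4% |
| 3 | 0 | 53/56 = 94.6% | 53/53 = 100% | 59/62 = 95.2% |
| 3 | 1 | 52/56 = 92.9% | 52/53 = 98.1% | 58/62 = 93.5% |
| 5 | 0 | 51/56 = 91.1% | 51/51 = 100% | 57/62 = 91.9% |
| 5 | 1 | 50/56 = 89.3% | 50/51 = 98.0% | 56/62 = 90.3% |

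The first two rows match under the SAP rules: one lost achiever costs the same as one relapse, 1/56 = 1.8 points of PPV and 1/62 = 1.6 points of agreement.

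**Share of the PPV shortfall due to missing data.** For missing rate m and relapse rate r (both assumed), share = m/(m + (1 − m)r). With m = 5% and r = 0.5%: 0.05/(0.05 + 0.95 × 0.005) = 91%. Over m = 2–10% and r = 0.2–2% the share runs from 51% to 98%.

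**Direction for agreement.** Suppose 4 of the 6 non-achievers were lost before Week 12.
- With k = 3, x = 0: SAP rules give 59/62 = 95.2%; observed pairs give (53 + 2)/55 = 100%. The SAP version is lower.
- With k = 0, x = 1: SAP rules give (55 + 6)/62 = 98.4%; observed pairs give (55 + 2)/58 = 98.3%. The SAP version is marginally higher.

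**NPV.** In both cases NPV is 6/6 under the SAP rules and 2/2 in observed pairs. A confirmed failure by Week 12 cannot reach SVR24, a subject lost early fails both, and a missing SVR12 value followed by one below LLOQ is moved to SVR12 success. Only unusual patterns of unconfirmed values can put a subject in the SVR12-failure, SVR24-success cell.

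**The case against.** The best defence is that the plan already separates relapse from dropout. Relapse24 is restricted to SVR12 achievers with data in the SVR24 window; apart from reinfection and unconfirmed values, its complement is close to an observed-data PPV. Missing SVR24 data has its own non-response category with counts and subject lists. Concordance is descriptive: it is outside the three numbered secondary endpoints, the testing sequence in SAP 10.2 and the objectives, and it has no success criterion. Using the same SVR status also keeps its table consistent with the reported rates.

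Most of that stands, and it limits the point. It does not remove it. Relapse24 yields neither agreement nor NPV, the non-response table does not show carried-back pairs, and the sensitivity analyses in SAP 10.6 concern SVR12 only. A reader could see PPV of 94.6% beside Relapse24 of 0%.

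A second objection is to replacing the planned version, and it is sound. Protocol 5.5.1 lets the investigator prescribe another regimen after on-treatment virologic failure, and SAP 6.3 drops values after new HCV treatment starts. A plain requirement for two observed values would discard genuine non-responders. It would also discard an achiever with no value in the SVR24 window whose next value is below LLOQ, which is itself evidence of maintained response.

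**Conclusion.** The point holds as a cheap improvement to a descriptive analysis. PPV and agreement as planned respond to missed visits exactly as they respond to late relapse, and no version based on observed pairs is planned. In the illustration, PPV falls from 100% to between 98.2% and 91.1% for one to five lost achievers without any relapse. Those counts, and the rates behind the 51–98% share, are assumptions.

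A reader might infer more than the documents support:

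- *That the measures capture dropout instead of durability.* True relapse still lowers PPV and agreement; with no missing data, PPV is clean. The SAP labels these measures concordance and analyses late relapse through Relapse24.
- *That imputation inflates agreement and NPV.* The net effect on agreement can go either way. NPV is near 100% largely by construction, and its point estimate did not move in the cases worked.
- *That all three measures have an ITT denominator.* Only agreement does. PPV and NPV are conditional, although imputed status decides who enters them.
- *That the efficacy conclusions are at risk.* The primary SVR12 test and the SVR24 test are unaffected.

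**What to change.** In SAP 10.4, keep the ITT version and add agreement, PPV and NPV among subjects with an HCV RNA value in both the SVR12 and SVR24 windows, without backward or missing-as-failure imputation. Retain subjects with documented virologic failure, including those who then start new HCV treatment, as observed non-responders. State that this version is the one used to interpret concordance. Report how many subjects were excluded for missing data and how many had a carried-back value.

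The cost is a few sentences in the SAP, one extra table and a somewhat smaller denominator. No new data are needed.

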## **10.5 Efficacy Subgroup Analysis**

The number and percentage of subjects with SVR12 across all subjects in the ITT population will be presented by the following subgroups:

- Age group ( $\geq 3 - 8$ ,  $\geq 9 - 11$ , and  $\geq 12 - 17$  years) and weight group (15 to 29 kg, 30 to 44 kg,  $\geq 45$  kg) at enrollment;

- HCV genotype and sub-genotype (1a, 1b, other 1, and 4);
- Prior HCV Treatment Experience (naïve, IFN-experienced)
- Prior IFN treatment response (among experienced) (prior non-responder, prior breakthrough, prior relapse, unknown, and interferon experienced-other);
- IL28B genotype (CC or non-CC), (CC, CT, or TT);
- Sex (male or female);
- Baseline fibrosis stage (F0-F1, F2, F3 or F4);
- Baseline HCV RNA level (< 800,000 IU/mL or  $\geq$  800,000 IU/mL; < median or  $\geq$  median);
- Race (Black versus non-black);
- Ethnicity (Hispanic/Latino versus none);
- Baseline height z-score (< -1, -1 to 1 or > 1);
- Drug compliance (< 80% versus  $\geq$  80%).
- Baseline creatinine clearance using the CC&G method for subjects at least 12 years old (< 50 mL/min,  $\geq$  50 mL/min);
- Baseline creatinine clearance using the Schwartz method for subjects from 3 to < 12 years old (< 60 mL/min/1.73 m^2,  $\geq$  60 mL/min/1.73 m^2)
- RBV dose modifications (yes/no).

The 2-sided 95% Wilson score confidence interval will be produced for each subgroup with at least 10 subjects.

In addition, stepwise logistic regression will be performed on virologic failure (on-treatment virologic failure or relapse) using subgroup variables as described above, if there are sufficient number of virologic failures. Some variables may be treated as continuous to decrease the chance of separation or quasi-separation and some variables may be eliminated if missing for too many subjects.

**10.6****Sensitivity Analysis for the Efficacy Endpoint of SVR12**

In addition to presenting the primary efficacy endpoint of SVR12 as described in Section 10.4, two sensitivity analyses of SVR12 will be presented using the two modified populations – mITT-GT and mITT-GT-VF.

**10.7****Additional Efficacy Analyses**

The following efficacy endpoints will be analyzed by formulation, age and weight group, and across all subjects on the adult formulation:

1. The percentage of subjects with virologic failure during treatment;
2. The percentage of subjects with Post-Treatment relapse (including Relapse12 as defined at the end of this section);
3. The percentage of subjects who relapsed after achieving SVR12 (**Relapse24**).
4. The percentage of subjects with HCV RNA < LLOQ at each post baseline visit during the Treatment Period (using data as observed);
5. The change from baseline to all post-baseline visits in Fibrotest score.

All rates of SVR, ALT normalization, virologic failure on treatment and relapse will be presented with 2-sided 95% confidence intervals using the Wilson's method. Imputations for missing data will be performed as described in Section 6.3 for analysis of SVR and relapse. All other endpoints will be presented using data as observed.

A summary of the subjects who completed treatment and relapsed (defined as **Relapseoverall**) will be prepared displaying the number of subjects relapsing overall and by SVR visit window (within the SVR4, SVR12, SVR24 windows or after SVR24 window), including the subject number and the SVR visit window corresponding to the first HCV RNA value of those indicating the occurrence of relapse. A similar listing will be prepared for subjects who prematurely discontinued treatment and relapsed after having HCV RNA < LLOQ at their Final Treatment Visit. A listing of subjects in the ITT

population excluded from the relapse denominator (e.g., study drug duration < 77 days for subjects assigned to 12 weeks of treatment) will be provided, as applicable.

Summary statistics (n, mean, SD, median, minimum and maximum) at each applicable visit and for change from baseline to each applicable visit will be provided by fibrosis stage and SVR12 for Fibrotest score.

## **10.8 Treatment Failures**

The number and percentage of subjects meeting each and any of the SVR24 and SVR12 non-response categories as defined in Section 10.1 will summarized by formulation, age and weight group, and across all subjects on the adult formulation along with the 2-sided 95% confidence interval using the Wilson's score method and a corresponding list of the subjects numbers.

## **10.9 Growth and Development**

The following growth and development endpoints will be calculated at applicable study visits.

- Growth rate at each post baseline visit (defined as change in height over change in age from the previous visit)
- Height z score
- Waist circumference
- Tanner staging

For growth rate, summary statistics (N, mean and SD together, median and range together) will be provided at each applicable post baseline visit for all and by gender for each pre-defined age group separately. For height z score, summary statistics (N, mean and SD together, median and range together) of height z score and summary statistics (N, mean and SD together, median and range together) of change from baseline will be provided over time at each applicable study visit for all and by gender each for pre-defined age group separately. Change from baseline in waist circumference, weight

and height will be summarized together with other vital signs such as temperature and blood pressure. Listings of Tanner staging for each applicable subject over applicable timepoints will be produced.

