**Investigational Products:**

Weight < 45 kg or eligible but not willing to swallow the adult formulations: Part 1	
paritaprevir	1.0 mg mini-tablet
ritonavir	1.0 mg mini-tablet
ombitasvir	0.3 mg mini-tablet
dasabuvir	3.08 mg mini-tablet
ribavirin	40 mg/mL oral solution
Weight <math>\geq 45</math> kg who are <math>\geq 12</math> to 17 years old and willing to swallow the adult formulations:	
ombitasvir/paritaprevir/r	12.5/75/50 mg tablet
dasabuvir	250 mg tablet
Ribavirin	200 mg tablet

Doses:	Part 1 Mini-Tablet:			
	Initial dosing based on body weight at time of Screening:			
		≥ 15 to 29 kg	≥ 30 to 44 kg	≥ 45 kg
	paritaprevir (QD)	50 mg	100 mg	150 mg
	ritonavir (QD)	35 mg	70 mg	100 mg
	ombitasvir (QD)	10 mg	15 mg	25 mg
	dasabuvir (BID)	100 mg	150 mg	250 mg
	Ribavirin solution	Per local label		
	Part 2:			
	Only adult formulation and RBV tablets if required will be provided to subjects who are in the ≥ 12 – 17 year old age group with weight equal and greater than 45 kg and willing to swallow the adult formulations.			
Mode of Administration:	Oral			
Reference Therapy:	Not applicable			
Dose:	Not applicable			
Mode of Administration:	Not applicable			
Duration of Treatment:	Part 1: Pediatric subjects will receive OBV, PTV, RTV, DSV with or without RBV for 12 weeks.			
	Part 2: Pediatric subjects will receive OBV, PTV, RTV with or without DSV and with or without RBV for 12 weeks or 24 weeks.			
Criteria for Evaluation:	Efficacy:			
	Plasma HCV RNA (IU/mL) will be assessed at each treatment and Post-Treatment Period visit in all three parts of the study.			
	Pharmacokinetic:			
	Plasma concentrations of OBV, possible OBV metabolites, PTV, possible PTV metabolites, DSV, DSV M1 metabolite, other possible DSV metabolites, RTV and RBV (if applicable) will be determined at each study visit for each subject for the treatment periods of Part 1 and Part 2.			
	Safety:			
	Safety and tolerability will be assessed by monitoring adverse events, physical examinations, clinical laboratory tests and vital signs. Growth and development will be assessed relative to age specific norms.			

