### **5.1.2 Safety Population**

All subjects who receive at least one dose of study drug in Part 1 or Part 2 will be included in the safety population, which will be the same as the ITT population for this study.

Safety analyses will be performed on the safety population by age group and overall among subjects on the mini-tablet formulation, by Part 1 vs Part 2 and overall among subjects on the adult formulation, and overall among all subjects (Safety Summary 7 column table).

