## 7.1 Demographic and Baseline Characteristics

Demographics include age, birth year, weight, height, BMI, height z score (height z score will be calculated using WHO published height-for-age z-score tables), and waist circumference as continuous variables, and sex, race, ethnicity, geographic region and country, age category ([ $\geq$  3 - 8 year old group], [ $\geq$  9 - 11 year old group], and [ $\geq$  12 - 17 year old group]), weight category 15 to 29 kg, 30 to 44 kg,  $\geq$  45 kg), and height z-score category (< -1, -1 to 1, > 1).

Baseline characteristics will include: HCV genotype subtype (1a, 1b, 1-other, and 4; using central laboratory results and final genotype/subtype results, see Section 10.10), IL28B genotype ([CC, CT, or TT] and [CC or non CC]), prior IFN treatment history (treatment-naïve or IFN-based treatment-experienced), response to prior IFN treatment (prior non responder {null responder, partial responder, or other unable to specify}, breakthrough, relapse, unknown and interferon experienced-other), baseline platelet count (continuous and [ $< 90 \times 10^9/L$ ,  $\geq 90 \times 10^9/L$ ], baseline albumin (continuous and [ $< 35$ ,  $\geq 35$  g/L]), baseline creatinine clearance using the Schwartz method for subjects from 3 to < 12 years old (continuous and [ $< 30$ ,  $\geq 30$  to  $< 60$ ,  $\geq 60$  to  $< 90$ ,  $\geq 90$  mL/min/1.73 m^2]) and using the CC&G method for subjects at least 12 years old (continuous; and [ $< 30$  mL/min,  $\geq 30$  –  $< 50$  mL/min,  $\geq 50$  –  $< 90$  mL/min,  $\geq 90$  mL/min]) baseline HCV RNA levels ([continuous (use log10 HCV RNA)] and [ $< 800,000$  IU/mL or  $\geq 800,000$  IU/mL]), baseline fibrosis stage (F0 - 1, F2, F3, F4), baseline Fibrotest score (continuous and [ $< 0.49$ ,  $0.49$  –  $0.58$ ,  $0.59$  –  $0.74$ ,  $\geq 0.75$ ]), baseline Child-Pugh score (non-cirrhotic, 5, 6, or  $> 6$ ), tobacco use (current, former, never or unknown) status, alcohol use (current, former, never or unknown) status, and baseline Tanner pubertal staging – genital (males only) (stages 1 - 5), breast (females only) (stages 1 - 5), and pubic hair development (stages 1 - 5).

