**11.4.2 Statistical Methods**

Vital signs will be summarized at each visit during the Treatment Period. The baseline value will be the last measurement on or before the day of the first dose of study drug. This same baseline value will be used for all change from baseline tables in the Treatment and Post-Treatment Periods.

Mean changes from baseline to each post-baseline visit, including applicable post-treatment visits, will be summarized for each vital sign parameter with the baseline mean, visit mean, change from baseline mean, standard deviation, minimum, median, and maximum.

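### Only height is referenced to age norms: with waist and weight as raw change and Tanner stage only listed, an effect on weight gain, body composition or pubertal timing cannot be told from normal growth in the planned summaries

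*SAP*

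**What the plan says.** The effect of treatment on growth and development is an objective of Part 3 (Protocol synopsis and Section 5.1). Protocol 5.1.4 names four measures: waist circumference, Tanner stage, standardised height and growth rate. The synopsis, under Criteria for Evaluation, adds: "Growth and development will be assessed relative to age specific norms".

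The planned analyses are:

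- **Height.** SAP 7.1 and 10.9 use a WHO height-for-age z score. The score and its change from baseline are summarised at each applicable visit, overall and by gender within age group.
- **Growth rate.** SAP 10.9 summarises it by gender within age group, without a norm.
- **Waist and weight.** SAP 10.9 sends "Change from baseline in waist circumference, weight" and height to the vital-sign tables. There, under SAP 11.4.2, "Mean changes from baseline to each post-baseline visit, including applicable post-treatment visits, will be summarized for each vital sign parameter", with means, SD, median and range.
- **Tanner stage.** Baseline stage is tabulated (SAP 7.1). After baseline, "Listings of Tanner staging for each applicable subject over applicable timepoints will be produced"; no summary is planned.

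The vital-sign tables use the safety layout of SAP 5.1.2: "Safety analyses will be performed on the safety population by age group" for mini-tablet subjects, by Part for adult-formulation subjects, and overall. Sex is not a column. BMI appears only among the baseline variables. Protocol 8.1.3 describes the same handling of waist, weight and Tanner stage.

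**The concern.** Most children in this age range gain weight and waist, and move through puberty, during three years of follow-up whatever the drug does. Without a control arm, the only yardstick is what is expected for a child of that age and sex. The plan applies that yardstick to height and to nothing else.

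For weight and waist, the reader will see a mean change with no expected value beside it. For puberty, the reader will have individual ratings but no count of children at each stage by sex and age, and no count of children who advanced. Two of the four named measures, plus weight, therefore cannot answer the Part 3 question in the form planned.

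**Working it through.** **1. Follow-up.** Treatment weeks plus 144 post-treatment weeks: 12 + 144 = 156 and 24 + 144 = 168, which reproduces the durations in SAP 4.2. In years, 156 × 7 / 365.25 = 2.99 and 168 × 7 / 365.25 = 3.22.

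**2. What raw weight change would show.** The documents give no norms, so the annual gains are assumptions. Raw change = annual gain × 2.99 × (1 − proportion of gain lost).

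| Assumed normal gain | No loss | 20% loss | 30% loss |
|---|---|---|---|
| 2 kg/year | +6.0 kg | +4.8 kg | +4.2 kg |
| 3 kg/year | +9.0 kg | +7.2 kg | +6.3 kg |
| 5 kg/year | +14.9 kg | +12.0 kg | +10.5 kg |

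A positive sign is not the issue, since any partial loss leaves a gain. The issue is that one figure fits several explanations. A mean of +7.2 kg is a 20% loss from 3 kg/year, but it is also an undisturbed gain of 7.2 / 2.99 = 2.4 kg/year, inside the assumed range. Waist behaves the same way: an assumed 1 to 3 cm/year gives about +3.0 to +9.0 cm, and 80% of that is +2.4 to +7.2 cm.

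**3. Who shares a column.** The adult-formulation total holds about 12 (Part 1) + 26 (Part 2) = 38 of 62 planned subjects, all aged 12 to 17. Boys and girls before, during and after the growth spurt enter one mean.

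**4. Tanner volume.** About 38 + 12 = 50 planned subjects are 9 or older at entry. With two scales at Day 1 and PT Weeks 12, 36, 96 and 144, the listing holds up to 50 × 2 × 5 = 500 ratings. It has gaps by design, because staging stops at Stage 5.

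**5. What a z score would add.** If study children track the reference, the expected change is 0. The documents give no SD for the change, so a range is assumed. The 95% half-width is t(0.975, n − 1) × SD / √n.

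| Assumed SD of change | n = 12 | n = 62 |
|---|---|---|
| 0.3 | 0.19 | 0.08 |
| 0.5 | 0.32 | 0.13 |
| 0.8 | 0.51 | 0.20 |

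The pooled estimate would be informative. A single age group of 12 would be informative only for larger shifts.

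**The case against.** The strongest reply is that growth is already measured against norms. Change in height z score removes expected linear growth without a control arm, and growth rate is also split by gender. This stands. A reader might infer that any harm to growth would be hidden, or that nothing in the plan separates drug effect from expected growth. The documents do not support that reading, because linear growth is covered.

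Other points also carry weight:

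- Weight is a vital sign, not one of the four named growth measures. Waist and Tanner stage are named.
- Protocol 5.3.4 ties only height to age, and SAP 10.9 follows Protocol 8.1.3. So the SAP does not depart from the protocol's statistical section; the mismatch is with the synopsis sentence.
- The tables show sizes as well as signs, and mini-tablet subjects are split by age group. This helps, but the expected size still appears nowhere.
- Expected growth is smaller at PT Weeks 12 and 36 than at Week 144. A proportional loss shrinks with it, so earlier visits do not resolve the ambiguity.
- A delayed child can be found in the Tanner listing, and a table would be sparse: 50 subjects over 2 sexes, 2 age groups and 5 stages average 2.5 per cell. The listing should stay. It is not a summary, however.
- Some adolescents will have finished growing, so not every child gains. That makes a pooled raw mean harder to read.

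**Conclusion.** The point holds for weight, waist and pubertal timing, not for linear growth. In the planned summaries, an effect on weight gain, body composition or pubertal timing cannot be told from normal growth, which falls short of the synopsis statement. Protocol 8.1.6.3 also promises criteria for potentially clinically significant vital signs during treatment; SAP 11.4 defines none, so no weight flag fills the gap.

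The durations are the documents' own. The kg, cm and SD values are assumptions for illustration, and the conclusion does not depend on their exact size. Growth is a Part 3 objective but is not among the primary or secondary objectives in Protocol 4.0, and no test or decision depends on it. This is a worthwhile, inexpensive improvement. A z score supplies an external reference, not a control: it would show departure from expected growth but would not by itself attribute that departure to the drug.

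**What to change.** In SAP 10.9:

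- Add BMI-for-age z score, specific to sex and age at visit, at Day 1 and PT Weeks 12, 36, 96 and 144, with change from baseline, by gender within age group as for height. Name the reference and state how ages beyond its range are handled: a subject enrolled at 17 will be about 20 or 21 at PT Week 144. Pair height and weight from the same date, because SAP Tables 4 and 5 give them different windows.
- Add waist-to-height ratio at the same visits, labelled as a size-adjusted description and not an age norm.
- Tabulate Tanner stage and shift from baseline by sex and age group for each scale, carrying Stage 5 forward because staging stops there.
- Keep the raw changes and the Tanner listing as descriptive output.
- Correct the height z score citation: reference 6 in the SAP is the peginterferon label, and the WHO standard is reference 7.

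The inputs are already collected, with no extra visit or procedure. The cost is some SAP wording, a few extra tables, and small cells for Tanner stage.
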